1 SUMMARY OF THE PROTOCOL

1.1 SYNOPSIS

Title:	Lifestyle Intervention Clinical Trial for the Remission of Type 2 Diabetes Mellitus in Primary Care (CREDOenAP) [Ensayo clínico de intervención estilo de vida para la reversión de Diabetes Mellitus tipo 2 en Atención Primaria (CREDOenAP)]
Grant Number:	N/A
Study Description:	Intervention program with intensive lifestyle counseling, added to standard pharmacological treatment subsequently adjusted according to clinical needs and outcomes. The intervention will last 6 months and consists of biweekly in-person and telephone visits. Patients will follow a personalized dietary plan with carbohydrate restriction, based on the recommendations of the American Diabetes Association; engage in moderate and accessible physical activity; implement circadian rhythm regularization; and receive psychological counseling and support.
Objectives*:	
Primary objective:
 
To quantify the proportion of Type 2 Diabetes (T2DM) remission among participants without evidence of absolute insulinopenia enrolled in the lifestyle intervention program (CREDOenAP) at the end of the program (6 months).
 
Secondary objectives:
 
- To quantify the percentage of T2DM remission among participants in the lifestyle intervention program (CREDOenAP) one year after completion of the program (18 months).- To determine the nutritional, physical activity, and quality-of-life patterns of participants in the CREDOenAP program before, at the end of the intervention and one year after (18 months).- To assess anthropometric, metabolic, and imaging markers of cardiovascular risk in participants in the CREDOenAP program before, at the end of the intervention (6 months) and one year after completion (18 months).

Endpoints^{*}:

Primary Endpoint:

- Percentage of participants achieving type 2 diabetes remission at 6 months, defined as HbA1c <6.5% after 6 months of intervention and at least 3 months without antidiabetic medication. HbA1c will be determined through fasting blood analysis (minimum 8 hours).
- Percentage of participants achieving T2DM remission at 6 months, defined as fasting venous plasma glucose <126 mg/dL after 6 months of intervention and at least 3 months without antidiabetic medication. Fasting glucose will be measured through venous blood analysis after a minimum 8-hour fast.

Secondary Endpoints:

- Percentage of participants maintaining type 2 diabetes remission at 18 months, defined as HbA1c <6.5% after 12 months post-intervention and at least 9 months without antidiabetic medication.
- Percentage of participants maintaining type 2 diabetes remission at 18 months, defined as fasting venous plasma glucose <126 mg/dL after 12 months post-intervention and at least 9 months without antidiabetic medication.
- Change in dietary patterns at 6 and 18 months, assessed using a validated 24-hour dietary recall questionnaire, to evaluate adherence to the nutritional component of the intervention.
- Change in physical activity level at 6 and 18 months, measured using the International Physical Activity Questionnaire (IPAQ).
- Change in health-related quality of life at 6 and 18 months, assessed using validated instruments such as the SF-36 or EQ-5D questionnaires.
- Change in cardiovascular risk factors at 6 and 18 months, including blood pressure, total cholesterol, HDL cholesterol, LDL cholesterol, Apo B100, triglycerides, and presence and size of carotid atherosclerotic plaques.
- Change in metabolic indicators at 6 and 18 months, including weight, Body Mass Index (BMI), waist

circumference, insulin resistance (HOMA-IR index), pancreatic beta-cell function (HOMA-B index), and fasting insulin.

Study Population: The study population consists of patients with type 2 diabetes (T2DM) assigned to the Primary Care centers of Barceloneta and Larrard at Parc Sanitari Pere Virgili, Barcelona.

Phase* or Stage: N/A.

[figure not shown]
Description of Sites/Facilities Enrolling Participants: Multicenter Study Sites
Barceloneta Primary Care Center, Parc Sanitari Pere Virgili, Barcelona, Spain
Larrard Primary Care Center, Parc Sanitari Pere Virgili, Barcelona, Spain

Description of Study Intervention/Experimental Manipulation: The program consists of biweekly in-person and telephone visits, focused on implementing a personalized dietary plan with carbohydrate restriction, based on the American Diabetes Association recommendations; moderate and accessible physical activity; circadian rhythm regularization; and psychological counseling and support.

Study Duration: 3 years.

Participant Duration: 18 months (6 months of intervention and follow-up assessments one year after completion of the intervention).

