3 OBJECTIVES AND ENDPOINTS

OBJECTIVES	ENDPOINTS	JUSTIFICATION FOR ENDPOINTS

Primary
 
To quantify the percentage of type 2 diabetes (T2DM) reversal among participants without signs of absolute insulinopenia enrolled in the CREDOenAP lifestyle intervention program at the end of the program (6 months).
	
Percentage of participants achieving type 2 diabetes (T2DM) remission at 6 months, defined as HbA1c <6.5% after 6 months of intervention and at least 3 months without antidiabetic medication. HbA1c will be measured from fasting venous blood samples (minimum 8 hours fasting).
 
Percentage of participants achieving T2DM remission at 6 months, defined as fasting venous plasma glucose <126 mg/dL after 6 months of intervention and at least 3 months without antidiabetic medication. Fasting plasma glucose will be measured from venous blood samples after a minimum 8-hour fast.
	
These measures allow evaluation of the intervention's efficacy, as they are widely accepted indicators of type 2 diabetes (T2DM) remission. These criteria have been consensually established and accepted by international organizations such as the American Diabetes Association (ADA) and the European Association for the Study of Diabetes (EASD).

Secondary		
1. To quantify the percentage of type 2 diabetes (T2DM) remission among participants in the CREDOenAP lifestyle intervention program one year after completing the program (18 months).	
Percentage of participants maintaining type 2 diabetes (T2DM) remission at 18 months, defined as HbA1c <6.5% after 12 months following the intervention and at least 9 months without antidiabetic medication.
 
Percentage of participants maintaining T2DM remission at 18 months, defined as fasting venous plasma glucose <126 mg/dL after 12 months following the intervention and at least 9 months without antidiabetic medication
	
These measures allow evaluation of the efficacy and long-term sustainability of the intervention, as they are widely accepted indicators of type 2 diabetes (T2DM) remission. These criteria have been consensually established and accepted by international organizations such as the American Diabetes Association (ADA) and the European Association for the Study of Diabetes (EASD).

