9 STATISTICAL CONSIDERATIONS

9.1 STATISTICAL HYPOTHESES

Primary Endpoint:

The primary hypothesis is based on the null hypothesis (H_0), which states that there is no difference in the percentage of type 2 diabetes (T2DM) remission between the intervention group and the control group. Conversely, the alternative hypothesis (H_1) states that the percentage of T2DM remission will be significantly higher in the intervention group compared to the control group. An efficacy analysis is planned and will be evaluated right after the end of the intervention.

Secondary Endpoints:

The null hypothesis (H_0) states that there will be no significant differences in the proposed secondary variables (metabolic, behavioral, and quality-of-life variables) between the intervention group and the control group. Conversely, the alternative hypothesis (H_1) states that there will be statistically significant differences in the proposed secondary variables (metabolic, behavioral, and quality-of-life variables), with more favorable outcomes for the intervention group compared to the control group. An efficacy analysis of the intervention is planned, and the evaluation will be carried out 12 months after the end of the intervention.

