9.2 SAMPLE SIZE DETERMINATION

Based on the primary variable of the intervention, the percentage of T2DM remission, the required sample size has been calculated to observe statistically significant differences. This variable will be coded dichotomously. A total of 120 volunteers (60 per arm) will be recruited for the study. Accepting an alpha risk of 0.05 (5%) and a beta risk of less than 0.2 in a two-sided test, at least 52 subjects in the control group and 52 subjects in the intervention group would be required to detect as statistically significant a 20% difference between two proportions (primary endpoint: T2DM remission). For the control group, the expected remission rate ranges from 0 to 5%, whereas in the intervention group, it is expected to be at least 25%. The remission rates have been benchmarked against previous studies (Lean et al., n.d.). An estimated loss to follow-up rate of 15% has been considered.

Given the estimated 15% loss to follow-up, the sample size has been increased to 60 participants instead of 52. This ensures that the statistical power of the analysis will be preserved.

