9.4 STATISTICAL ANALYSES

9.4.1 GENERAL APPROACH

The statistical analysis will consist of two sub-analyses. First, a descriptive analysis will be performed, followed by an analysis to determine differences between the intervention and control groups. These analyses will be conducted using STATA/MP statistical software.

In the initial descriptive analysis, qualitative variables (e.g., sex, socioeconomic status) will be described using absolute and relative frequencies. Continuous variables (e.g., age, HbA1c, weight, BMI, blood pressure, cholesterol, HOMA-IR) will be described using mean and standard deviation for normally distributed variables, or median and interquartile range for variables with non-normal distributions. Normality of quantitative variables will first be assessed using the Kolmogorov-Smirnov test. Group comparability will be assessed using standardized mean differences (SMD), with $SMD < 0.10$ indicating negligible imbalance and $SMD \geq 0.20$ indicating meaningful imbalance. Formal hypothesis testing at baseline will not be routinely performed; if included, such p-values will be reported as descriptive only.

The primary efficacy analysis will use analysis of covariance (ANCOVA), with the 6-month value of the primary outcome as the dependent variable and the baseline value as a covariate. The model will include prespecified covariates: baseline outcome, age, sex, site (if applicable), and block/stratum used in randomization. The primary result will be the adjusted mean difference between intervention and control. Absolute risk reduction, relative risk reduction, and number needed to treat will also be calculated.

The secondary efficacy analysis will be a longitudinal analysis. The effect of the intervention in terms of T2DM reversal or remission (dichotomous variable) will be estimated using a mixed-effects model for repeated measures (MMRM) with a random intercept for participant and fixed effects for time, group, and group \times time interaction.

All statistical tests will be two-sided, with a significance level of $\alpha = 0.05$ considered statistically significant.

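### The protocol lists two 6-month primary remission endpoints, sizes for one, gives no success rule, and names a third primary endpoint in 9.4.2

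*Protocol*

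**What the plan says.** **Two endpoints.** The synopsis (1.1) lists under its primary endpoint heading both "Percentage of participants achieving type 2 diabetes remission at 6 months, defined as HbA1c <6.5% after 6 months of intervention" and "Percentage of participants achieving T2DM remission at 6 months, defined as fasting venous plasma glucose <126 mg/dL after 6 months of intervention". Each also requires at least 3 months without antidiabetic medication. The table in section 3 repeats both, the first as "Percentage of participants achieving type 2 diabetes (T2DM) remission at 6 months, defined as HbA1c <6.5% after 6 months of intervention". Section 8.1 repeats both again under the primary outcome variables.

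**One variable.** Section 9.1 has a single null hypothesis, that "there is no difference in the percentage of type 2 diabetes (T2DM) remission between the intervention group and the control group", and names no criterion. Section 9.2 opens: "Based on the primary variable of the intervention, the percentage of T2DM remission, the required sample size has been calculated". It adds that this variable is coded dichotomously.

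**Error rate.** Section 9.4.1 states: "All statistical tests will be two-sided, with a significance level of" 0.05. The only sentence on multiplicity is in 9.4.7 and concerns subgroups.

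**A third candidate.** Section 9.4.2 names the change in HbA1c from baseline to 6 months as the primary endpoint, analysed by ANCOVA. Section 9.4.1 also makes ANCOVA the primary efficacy analysis and calls the remission model the secondary one. Section 9 never mentions the fasting-glucose endpoint.

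**Other definitions.** Section 2.1 defines remission by HbA1c alone, and so does 9.4.3 for 18 months. Section 6.1.1 also uses HbA1c alone but asks for a value below 6.5% over at least 6 months. Section 2.2 names both measures and then joins the two thresholds with an or.

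**The concern.** The number and identity of the primary endpoints decide what a positive trial means. With two listed, one tested and sized, and a third analysed, the protocol does not settle this.

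If success on either remission criterion could carry the claim at 0.05, the chance of a false positive would exceed 5%. If both had to succeed, a sample size worked out for one variable could fall short of its promised power. And if 9.4.2 is followed literally, neither remission endpoint has a primary test at 6 months, although 9.1 states the hypothesis about remission and 9.2 sizes the trial for it.

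**Working it through.** **Inputs from 9.2.** The error rates are stated as follows: "Accepting an alpha risk of 0.05 (5%) and a beta risk of less than 0.2 in a two-sided test". On the control arm: "For the control group, the expected remission rate ranges from 0 to 5" per cent (5% used here). The intervention arm is at 25% or more. The section asks for 52 per arm, raised to 60 for 15% loss. Losing 15% of 60 leaves 60 × 0.85 = 51.

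**Assumption.** The protocol gives no correlation between the two remission definitions. I use a phi coefficient, the same in both arms, with P(both met) = p² + phi·p(1 − p), and vary it.

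**Step 1: the plan's own figure, one endpoint.** With a pooled mean of 0.15:

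- n = [1.96·√(2·0.15·0.85) + 0.842·√(0.05·0.95 + 0.25·0.75)]² / 0.20² = (0.990 + 0.408)² / 0.04 ≈ 48.8, so 49 per arm.
- Power at n is Φ[(0.20·√n − 0.990) / 0.485]. This gives 82.5% at 52, 81.7% at 51 and 87.6% at 60.

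This formula does not return 52 exactly. The arcsine formula divided by 0.85 does (44.17 / 0.85 = 51.96). Either way, 52 per arm supports the promise of beta below 0.2 for one endpoint.

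**Step 2: either endpoint may succeed, no true effect.** For two independent tests the limit is 1 − 0.95² = 9.75%. I simulated 400,000 trials per setting with the pooled two-proportion test:

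| Null rate | n per arm | phi 0 | 0.4 | 0.6 | 0.8 | 0.9 |
|---|---|---|---|---|---|---|
| 5% | 51 | 8.6% | 8.2% | 7.8% | 6.8% | 6.0% |
| 5% | 60 | 8.9% | 8.7% | 8.2% | 7.2% | 6.2% |
| 25% | 51 | 9.9% | 9.6% | 9.0% | 7.9% | 7.1% |
| 25% | 60 | 10.2% | 9.7% | 9.1% | 8.1% | 7.3% |

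The single test itself runs at about 4.4–4.6% at a 5% rate and 5.1–5.3% at 25%. That is why one cell exceeds 9.75%. These are two-sided figures. In the normal approximation, false findings in the favourable direction alone are half as frequent: 4.9% at zero correlation between the test statistics and 3.5% at 0.9, against a nominal 2.5%.

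**Step 3: both endpoints must succeed, 5% against 25% on each.** Same simulation:

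| n per arm | One endpoint | phi 0.4 | 0.6 | 0.8 | 0.9 |
|---|---|---|---|---|---|
| 51 | 0.84 | 0.74 | 0.76 | 0.785 | 0.80 |
| 60 | 0.90 | 0.82 | 0.84 | 0.855 | 0.87 |

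The bivariate normal approximation is a little lower because it starts from 81.7% rather than 84%. At 51 per arm it gives 71% at a correlation of 0.5 and 77% at 0.9. At 60 it reaches 80% once the correlation is about 0.6.

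**Step 4: one variable only.** With HbA1c alone, or one composite fixed in advance, there is one test at 0.05. Step 1 then applies unchanged, provided the assumed rates hold for that variable.

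**The case against.** The strongest reply is that the protocol intends one variable. The synopsis heading is singular, 8.1 gives one outcome (presence of remission) with two sub-items, 9.1 has one null hypothesis, and 9.2 has one dichotomous variable. The and/or wording in 2.2 describes an external consensus, not the trial's decision rule. This has force, and it rules out the stronger reading a reader might infer, that the error rate or the power must be wrong. Under HbA1c alone or a defined composite, neither is. But the protocol does not say which single variable it means, and 1.1 and 3 give each criterion its own complete endpoint statement.

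The second reply is about size. Both definitions share the medication-free condition, so the correlation is probably high and the extremes near zero are unlikely. A null rate of 25% also lies well above the expected control rate. With 60 evaluable per arm the both-required power meets the promise in simulation, and at 51 per arm the gap closes at phi 0.9. All of this stands and is reflected in the ranges given.

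Third, an alpha allocation is often placed in the SAP, which is not shown. It would therefore go too far to say that the rule will be chosen after unblinded results are seen. Nor do the documents show that each remission endpoint will in fact be tested as primary, since 9.4.2 tests neither. What stands is that the protocol's own sections disagree on what is primary.

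**Conclusion.** The point holds as an internal contradiction. Sections 1.1, 3 and 8.1 have two primary remission endpoints, 9.1 and 9.2 have one unnamed remission variable, and 9.4.2 has a continuous endpoint that is neither. No rule connects them.

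The numerical effect is conditional on the rule and on the assumed correlation:

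- **Either may succeed:** false-positive risk of about 6–10%, or about 6–9% at a 5% null rate.
- **Both must succeed:** power of about 0.74–0.80 at 51 per arm for phi 0.4–0.9, and above 0.80 at 60.
- **HbA1c alone or one defined composite:** no effect on either figure.

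The sizes are moderate. The matter still needs settling because it concerns the trial's main claim and the correction is one of wording.

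**What to change.** - Name one primary endpoint: HbA1c-defined remission at 6 months (HbA1c below 6.5% and at least 3 months without antidiabetic medication), tested at two-sided 0.05. This is the criterion already used in 2.1 and, for 18 months, in 9.4.3.
- Move glucose-defined remission to the secondary endpoints as a supportive estimate.
- Write the same variable into 1.1, 3, 8.1, 9.1 and 9.2.
- Align 9.4.1 and 9.4.2 so that the primary analysis compares this binary outcome between groups, for example by the covariate-adjusted logistic model already in 9.4.3, with a risk difference. At 0–5% control remission only 0 to 3 events are expected among 60 controls, so the covariate list should be short. HbA1c change by ANCOVA becomes secondary.
- Reconcile the remission wording in 6.1.1 (HbA1c below 6.5% for at least 6 months) with this definition.

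A single composite defined in advance would also resolve the multiplicity question, but HbA1c alone needs the least rewriting.

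**Cost:** wording in about eight sections and the matching registry entry, with no extra patients or data. The fasting-glucose definition loses its primary status.

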1.2 SCHEME

1.3 SCHEDULE OF ACTIVITIES

	Screening / Selection	Assessment 1	Visit 1: Carotid ultrasonography + laboratory analyses	Randomization	Visit 2: Intervention session	Visits 3 to 15: Biweekly telephone contacts	Assessment 2 (6 months)	Assessment 3 (18 months)	End of study
Assessment of inclusion/exclusion criteria	X								
Signing of informed consent		X							
Collection of sociodemographic variables		X							
Review of medical history and current medication		X						X	
Anthropometric measurements (weight, height, BMI, waist circumference)		X					X	X	
Health-related quality of life questionnaire (SF-36)		X					X	X	
Dietary questionnaire (24-hour recall)		X				X	X	X	
Physical activity questionnaire (IPAQ)		X					X	X	
Laboratory analyses (HbA1c, glucose, insulin, lipids, etc.)			X				X	X	
Imaging studies (Carotid ultrasonography)			X				X	X	
Randomization				X					
Adverse event recording		X					X	X	X
Telephone follow-up for clinical status						X			

2 INTRODUCTION

2.1 STUDY RATIONALE

Type 2 diabetes (T2DM) represents a major public health problem, with its incidence rapidly increasing worldwide. In 2014, 8.5% of the global population was affected by this disease. (Hambleton *et al.*, 2013). The results of *Diabetes* (Soriguer *et al.*, 2012), the largest epidemiological study conducted in Spain revealed a prevalence of 13.8% for type 2 diabetes among adults over 18 years of age (5.3 million people), of whom 43% (2.3 million) were undiagnosed at the time of the study. Traditionally, type 2 diabetes (T2DM) has been considered a progressive and irreversible disease. This hypothesis was supported by a series of studies showing that 50% of individuals required insulin therapy 10 years after T2DM diagnosis, along with a progressive loss of insulin production. (“Effect of Intensive Blood-Glucose Control with Metformin on Complications in Overweight Patients with Type 2 Diabetes (UKPDS 34). UK Prospective Diabetes Study (UKPDS) Group.,” 1998; “U.K. Prospective Diabetes Study 16. Overview of 6 Years’ Therapy of Type II Diabetes: A Progressive Disease. U.K. Prospective Diabetes Study Group.,” 1995; Rudenski *et al.*, 1988). However, these hypotheses were based on studies with small sample sizes (Rahier *et al.*, 2008; Rudenski *et al.*, 1988) or on data from groups of individuals who gained weight steadily (approximately 5 kg in the intensively treated group (“Effect of Intensive Blood-Glucose Control with Metformin on Complications in Overweight Patients with Type 2 Diabetes (UKPDS 34). UK Prospective Diabetes Study (UKPDS) Group.,” 1998; “U.K. Prospective Diabetes Study 16. Overview of 6 Years’ Therapy of Type II Diabetes: A Progressive Disease. U.K. Prospective Diabetes Study Group.,” 1995). However, this paradigm has been shifting due to new evidence suggesting that intensive lifestyle interventions can achieve reversal or remission of the disease.

The objective of this study is to evaluate the effectiveness of the CREDOenAP program (Counseling for the Reversal of Diabetes in Primary Care), a multicomponent intervention based on intensive lifestyle modification, implemented in the primary care setting. The program focuses on four key pillars: a carbohydrate-restricted diet based on whole foods, daily physical activity, smoking and alcohol cessation, and psycho-emotional support (Committee ADAPP, 2021).

The intervention program is based on both WHO and ADA recommendations to address physical inactivity, diet, smoking, and alcohol consumption, as well as local dietary habits, prioritizing fresh, whole, locally sourced foods rather than processed, prepackaged, or substitute products. The program will utilize the usual resources of Family and Community Medicine, including standard in-person consultations and telehealth (“5. Facilitating Behavior Change and Well-Being to Improve Health Outcomes: Standards of Medical Care in Diabetes—2022,” 2022; Committee ADAPP, 2021).

It is expected that the changes induced by this intervention will result in improved glycemic control and, ultimately, partial or complete remission of type 2 diabetes (T2DM), defined according to the American Diabetes Association (ADA) consensus criteria as HbA1c <6.5% without pharmacological treatment for at least 3 months (“6. Glycemic Targets: Standards of Medical Care in Diabetes—2022,” 2022). In addition to potential T2DM remission, improvements in body

weight and cardiovascular risk profile are also anticipated, which may translate into reduced utilization of healthcare services and resources (*Committee ADAPP, 2021*).

It should also be noted that, to date, no methodology for T2DM reversal has been evaluated in patients under primary care follow-up in our setting and following a real-food diet. Developing such interventions and assessing their effectiveness is crucial for a systematic, multicomponent approach based on evidence-based medicine principles, adding value to routine primary care practice.

